27.0 SAMPLE SIZE CALCULATION

The sample size was calculated based on available participant populations.

FFP has long been an approved medication in the US. This study addresses the potential benefits of FDA approved [21CFR640.30] Plasma exclusively collected from 18 – 25 year old volunteer donors.

28.0 COMPLIANCE AND WITHDRAWAL

Subject compliance

Compliance will be measured by attendance at infusion visits and tolerance of entire prescribed infusion.

Treatment cessation

Patients who develop an unexpected new condition precluding further participation will be withdrawn from receiving further infusions.

29.0 WITHDRAWAL OF PARTICIPANTS

Study drug must be discontinued for the following:

1. The participant decides he/she no longer wishes to continue
2. Withdrawal is recommended by the Investigator or another clinician (for example, intercurrent illness during course of study or side effects from study drug)
3. The trial is terminated at the request of the Co-Investigator

Patients will be discontinued for the following:

**INTRAVENOUS young FRESH FROZEN PLASMA (yFFP®) INVESTIGATIONAL TREATMENT FOR
PARKINSON'S DISEASE
PROTOCOL FOR CONTROLLED STUDY**

Patient is randomized, but never receive any medicine (that is, the first infusion is never started - this is also termed 'non-compliance')

Participants have the right to withdraw from the study at any time and for any reason without providing a reason. The investigator also has the right to withdraw participants from the study if they consider that it is in the best interests of the participant. Should a participant decide to withdraw from the study, he/she will be asked to volunteer a reason for withdrawal but are at liberty not to state a reason.

Should a participant withdraw from study drug only, efforts will be made to continue to obtain follow-up data with the permission of the patient. Subjects who withdraw from treatment early will be encouraged to return to the study site for follow-up, providing that consent is not withdrawn.

30.0 DATA MONITORING, QUALITY CONTROL AND QUALITY ASSURANCE

This protocol has been developed by clinicians.

Day to day management of study will be the responsibility of the Co-Investigator with the assistance of the Trial Manager.

[name]: Principal Investigator

[name]: Co-Investigator

[name]: Co-Investigator

[name]: Trial Manager (TM)

[name]: Data Manager (DM)

The TM will arrange telephone conferences and provide weekly recruitment email updates during recruitment and status reports.

The TM & DM will organize a meeting for all Investigators (and for key staff working on the study) to sign the protocol, and to agree on the content and undergo training on SOPs before the start of recruitment.

A second investigators' meeting will be held at the end of 12 weeks to review the results. A final meeting will be held at the conclusion of the study at 24 weeks.

The Co-Investigators will be responsible for the day-to-day study conduct at site. This includes establishing and carrying out the trial at his/her center in accordance national and local law and public health regulations and FDA.

**INTRAVENOUS young FRESH FROZEN PLASMA (yFFP®) INVESTIGATIONAL TREATMENT FOR
PARKINSON'S DISEASE
PROTOCOL FOR CONTROLLED STUDY**

They will ensure that all site-specific documentation is complete and correct; and that all staff involved in the trial are compliant with regulations, and that they are appropriately trained in those aspects relevant to their role in the study while being familiar with the trial protocol.

Co-Investigators are also responsible for managing recruitment on target and collecting and submitting accrual and outcome data in a timely manner; responding in timely fashion to requests from the sponsor for information; providing and responding promptly to SAEs and agreeing to monitoring audit visits by Quality Assurance as required.

Central and site monitoring of study conduct, and data collected will be performed by the Trial Manager on behalf of the Sponsor. Full details will be documented in a monitoring plan, agreed upon with the study sponsor. The main areas of focus will include:

- Consent
- Serious adverse events
- Essential documents
- Drug accountability and management.

All monitoring findings will be reported and followed up with appropriate persons in a timely manner.

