7.0 STUDY DESIGN & METHOD

The study is a prospective double-blind placebo-controlled trial, designed to evaluate the safety and efficacy of intravenous young Fresh Frozen Plasma at 12.5 ml/kg in each of two doses, two days apart (25 ml/kg total).

Patients in the Placebo group will receive infusions of 0.9% Sodium Chloride with Vitamin B2 at a volume rate equal to that of yFFP 12.5 ml/kg in each of two doses, also two days apart.

Consecutive patients are alternately assigned to one of the two treatment study groups, labeled 'yFFP' or 'Saline' group. Because yFFP is in short supply,

**INTRAVENOUS young FRESH FROZEN PLASMA (yFFP®) INVESTIGATIONAL TREATMENT FOR
PARKINSON'S DISEASE
PROTOCOL FOR CONTROLLED STUDY**

the trial manager is free to change the strict alternate allocation sequence, according to the blood types of yFFP available.

Each participant's condition will be classified as mild to moderate. Patients above 2.5 on the Hoehn and Yahr scale will not be eligible for the trial.

The primary outcome is the change in sum of the UPDRS scales 1-3 in the yFFP group compared with the placebo group.

There will be one study site, a secondary care clinic specializing in neurology and infusions (Houston, Texas).

Study will include 20 patients with Parkinson's disease.

Blinding will be achieved by preparing both yFFP and placebo (0.1% Riboflavin in normal saline) solution into identical bags. The Riboflavin is added to achieve indistinguishable color when compared to the yFFP. Labels, barcoded numbers and expiration dates for both the active and saline placebo will be indistinguishable. All infusion bags will be masked.

For the time frame, study day 0 is defined as the day of treatment allocation. Baseline evaluation and laboratory testing will be done then. The first infusion will be scheduled at most two weeks later, and the second infusion will occur two days after the first.

Physician assessments, caregiver surveys and blood tests will be completed at 4-weeks, 12-weeks and 24 weeks, to explore the duration of yFFP - and unspecific treatment effects.

Definition of end of study

The end of the study will be the last participant's final contact at 24 weeks.

The study duration will be eight months from study set-up to analysis and closure. An interim report will be produced at the 12-week point.

Serious Adverse Events (SAE) will be monitored for 14-days after final dose of yFFP or until resolution.

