20.0 ALLOCATION

Identification and allocation of patients

A patient identification number will be assigned after consent has been signed.

Patients will be allocated to placebo or yFFP (ratio 1:1) by Trial Manager.

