21.0 BLINDING

In the event of an urgent need to unblind treatment, call the Trial Manager.

If unblinding occurs, details including patient study number, the date performed, people involved, and the reason for the unblinding, shall be recorded by the administering nurse and retained.

If clinically indicated, the participant will be withdrawn from the medication.

Accidental unblinding's will be dealt with on a case by case basis if and when they arise. The patient's data should continue to be collected according to the visit schedule, even in the event of unblinding or withdrawal from study medication, unless the patient refuses.

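### The 12-week interim report and investigators' meeting fall before most or all week-24 primary UPDRS ratings, and nothing limits them to pooled or masked data

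*Combined protocol and SAP*

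**What the plan says.** Section 7 describes a double-blind, placebo-controlled trial at one site with 20 patients, 10 per arm. Bags and labels are matched so that the two products look alike. On follow-up it says: "Physician assessments, caregiver surveys and blood tests will be completed at 4-weeks, 12-weeks and 24 weeks". Section 26 takes the primary comparison from baseline to 24 weeks and mentions 12-week scores as possible input to a longitudinal model, so the plan expects UPDRS data at 12 weeks.

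Two sentences create the interim step. Section 7: "An interim report will be produced at the 12-week point". Section 30: "A second investigators' meeting will be held at the end of 12 weeks to review the results". A separate final meeting follows at 24 weeks.

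On roles, Section 30 makes the Co-Investigators responsible for "collecting and submitting accrual and outcome data in a timely manner". It also says: "Day to day management of study will be the responsibility of the Co-Investigator with the assistance of the Trial Manager". Section 20 says: "Patients will be allocated to placebo or yFFP (ratio 1:1) by Trial Manager".

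On timing, Section 7 says: "The study duration will be eight months from study set-up to analysis and closure".

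**The concern.** UPDRS scoring involves judgement. The trial's protection against expectation entering those scores is that whoever scores does not know the arm. The plan masks the product carefully, then schedules a review of results by investigators part-way through, without saying what they may see.

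Group means alone would not tell a rater which arm a given patient is in. By-arm tables or patient-level listings could, because there are only 20 patients and Section 7 assigns consecutive patients alternately, subject to changes for plasma availability. Once one patient's arm is known or guessed, the sequence points to others. If that happened before week 24, expectation could enter the primary outcome and no analysis could remove it afterwards.

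**Working it through.** **Step 1: does any other text close the gap?** The nearest safeguards are these.

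| Section | What it covers | What it leaves open |
|---|---|---|
| 7, 11, 13 | Appearance, labels and masking of bags | Results |
| 21 | Urgent and accidental unblinding | Planned review of results |
| 22 | Password access to the database for authorised study staff | That group is not defined and raters are not excluded |
| 24 | Where the analysis is run | Who receives the output |
| 25, 26 | A full SAP is deferred; Section 26 outlines the UPDRS analysis | The interim report is not mentioned |
| 37 | SAE notices worded so as not to unblind investigators | Efficacy results |
| 41 | When participants learn their arm | Investigators and raters |

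None states whether the 12-week results are pooled, masked or by arm, or who receives them.

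**Step 2: how many primary ratings follow the review?** The plan gives no figure to reproduce.

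Inputs from the documents: eight months in total, 24 weeks of follow-up, a review at 12 weeks, 20 patients.

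Assumptions: day 0 of the 20 patients evenly spaced over the enrolment window W; set-up plus analysis S = 0 or 4 weeks; time to compile the report L = 0, 2 or 4 weeks; review held once the last patient has reached week 12.

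- Eight months = 8 × 30.4375 / 7 = 34.79 weeks.
- W = 34.79 − 24 − S = 10.79 weeks (S = 0) or 6.79 weeks (S = 4).
- Review at W + 12 + L after the first day 0.
- Patient i (i = 0 to 19) has day 0 at W × i / 19. The primary rating is already done if W × i / 19 + 24 ≤ W + 12 + L.

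Example with S = 0, L = 4: the condition is 10.79 × i / 19 ≤ 10.79 − 12 + 4 = 2.79, so i ≤ 4.9. Five ratings are done and 15 are still to come.

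Primary ratings still to come, out of 20:

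| Scenario | S | L = 0 | L = 2 | L = 4 |
|---|---|---|---|---|
| Eight months | 0 | 20 | 18 | 15 |
| Eight months | 4 | 20 | 20 | 20 |
| Eight months, week-24 visits 2 weeks early (assumed) | 0 | 18 | 15 | 11 |
| Same | 4 | 20 | 20 | 17 |
| Ten months = 43.48 weeks (assumed overrun) | 0 | 12 | 10 | 8 |
| Same | 4 | 15 | 13 | 10 |

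If the 12 weeks are instead counted from the first patient's day 0, the review comes 24 − 12 = 12 weeks before the first primary rating and all 20 are still to come.

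**Step 3: what would a bias do?** The documents give no bias size, SD or alpha, so this only illustrates sensitivity. Take a two-sided 5% t-test (assumed), 10 per arm, 18 degrees of freedom and no true effect. A between-arm rating bias of b SD gives a noncentral t with noncentrality b × √(10/2). For b = 0.1, 0.25, 0.5 and 1.0 (all assumed), the false-positive rate is about 5.5%, 8.3%, 18.5% and 56.2%.

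**The case against.** The strongest reply is that nothing here plans an unblinding. Neither the report nor the meeting is described as by arm, the trial is called double-blind, and Section 37 takes care not to unblind investigators through SAE notices, so the intent is evident. That stands. A reader might infer that the plan shows investigators by-arm results at 12 weeks; the documents do not support this.

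Second, the rater is not identified. Collecting and submitting outcome data is not the same as scoring UPDRS, and attendance of the assessing physicians at the meeting is inferred from roles. That also stands, although there is one site and no separate blinded rater is described.

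Third, Section 21 says: "In the event of an urgent need to unblind treatment, call the Trial Manager". This suggests that site clinicians do not hold the allocation list. It is a fair inference, but the same Trial Manager allocates patients and assists the Co-Investigator day to day, and no sentence bars raters from the list.

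Fourth, the SAP deferred by Section 25 or the monitoring plan mentioned in Section 30 may settle who sees interim results. They may, and the text available lacks Sections 4 and 42. The claim is therefore limited to the text at hand.

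Fifth, the timing figures count ratings after a meeting of unknown content and do not measure harm. That is correct; they show only how much of the primary outcome could be exposed.

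**Conclusion.** The point holds in limited form and should be fixed. The plan schedules a review of results by investigators, some of whom are responsible for outcome data, before most or all primary ratings, and no text at hand restricts what they see. Under the stated eight months and the assumptions above, 15 to 20 of 20 ratings follow the review. The range is 11 to 20 with early week-24 visits and 8 to 15 with a ten-month overrun. Whether any rating would actually be biased, and by how much, cannot be derived from the documents. Confidence is moderate, because by-arm display and attendance by raters are inferred.

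A reader might also infer from Section 19 that the plan builds in a second unblinding, because its urine pregnancy test is tied to receipt of yFFP. That is too strong. The sentence is unfinished, the term may loosely mean study treatment (as it seems to in the SAE sentence of Section 7), and with entry at age 45 and above it reaches few if any patients. It merits a side note only.

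**What to change.** - Sections 7 and 30: state that the 12-week report and meeting show investigators, and anyone who rates patients, only pooled, masked efficacy data, and that by-arm results are withheld from them until the last week-24 rating is entered and verified against source.
- Section 21: state that UPDRS raters have no access to the allocation list or to by-arm results before then.
- Side note, Section 19: complete the sentence and reconcile it with the blind so that it does not depend on allocation.

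The cost is a few sentences and no change of design. The downside is that investigators wait until the last week-24 rating for by-arm results. Section 5 lists the trial as closed in January 2019, so new wording cannot alter past conduct. The sponsor can still state in the trial report what was shown at 12 weeks, to whom, and whether any of them rated patients afterwards.

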31.0 DIRECT ACCESS TO SOURCE DATA AND DOCUMENTS

The investigators agree to provide full access to all source data, study data and materials to the sponsor for purposes of monitoring, audit or inspection.

32.0 PHARMACOVIGILANCE

Refer to AABB Circular of Information

33.0 UNEXPECTED ADVERSE REACTIONS

Adverse event reporting will be in compliance with FDA. Most adverse drug reactions that occur in this study, whether serious or not, will be expected treatment-related side effects as FFP has a well-established side-effect profile and approximately 20% of all blood plasma transfused is from 18-25 year old donors (yFFP).

FFP can cause adverse reactions such as:

- Chills, headache, fever, vomiting, allergic reactions, nausea, arthralgia, low blood pressure and mild back pain, which may occur occasionally.

**INTRAVENOUS young FRESH FROZEN PLASMA (yFFP®) INVESTIGATIONAL TREATMENT FOR
PARKINSON'S DISEASE
PROTOCOL FOR CONTROLLED STUDY**

- Increase in serum creatinine level and/or acute renal failure have been observed.
- Very rarely, thromboembolic reactions, such as myocardial infarction, stroke, pulmonary embolism, and deep vein thromboses have occurred.

Details of further spontaneously reported adverse reactions include the following:

- Cardiac disorders: angina pectoris (very rare)
- General disorders and administrations site conditions: rigors (very rare)
- Immune system disorders: anaphylactoid shock (very rare), hypersensitivity (very rare)
- Blood pressure decreased (very rare)
- Musculoskeletal and connective tissue disorders: back pain (very rare)
- Respiratory, thoracic and mediastinal disorders: Dyspnea NOS (very rare);
or
- Vascular disorders: shock (very rare).

The adverse events reported above are expected in the sense that they are possible known side-effects of the study medication, but all reported instances of both serious and non-serious adverse events will be reported in this study.

During the trial, investigators will be made aware of any updates to the summary of product characteristics (SPC) but the protocol need not be amended every time there is a change unless it directly affects the study conduct. The source of accurate information regarding the active medication must always be the SPC and not the study protocol, and the above information is provided to reflect the situation at study start only.

34.0 PROTOCOL SPECIFICATIONS

For purposes of this protocol

1. Any serious adverse events will be recorded throughout the duration of the trial until 14 days after cessation of study drug or until resolution.
2. Non-serious adverse events will be recorded throughout duration of trial until 14 days after cessation of study drug.
3. Serious adverse events exclude any pre-planned hospitalizations not associated with clinical deterioration.

35.0 RECORDING AND REPORTING SERIOUS ADVERSE EVENTS OR REACTIONS

All adverse events and all serious adverse events should be recorded. Depending on the nature of the event, the reporting procedures below should be followed.

**INTRAVENOUS young FRESH FROZEN PLASMA (yFFP®) INVESTIGATIONAL TREATMENT FOR
PARKINSON'S DISEASE
PROTOCOL FOR CONTROLLED STUDY**

Any questions concerning adverse event recording/reporting should be directed to the Trial Manager in the first instance.

36.0 NON-SERIOUS ADVERSE EVENTS

All non-serious adverse events will be recorded on the "Patient infusion log". Severity of all AEs will be graded on a three-point scale of intensity (mild, moderate, or severe):

Mild: Discomfort is noticed, but there is no disruption of normal daily activities.

Moderate: Discomfort is sufficient to reduce or affect normal daily activities.

Severe: Discomfort is incapacitating, with inability to work or to perform normal daily activities.

Relation of an AE to treatment should be assessed by the investigator/delegate (must be a clinician) on-site. Investigators will be responsible for managing all adverse events according to local protocols, as the study blood product is already approved for use in other indications.

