8.0 SECONDARY OBJECTIVES

Secondary objectives: are to achieve a better understanding of this technology including the following:

- Factors predicting a beneficial response
- Effects on additional outcome parameters quality of life, and short-term risk profile

**INTRAVENOUS young FRESH FROZEN PLASMA (yFFP®) INVESTIGATIONAL TREATMENT FOR
PARKINSON'S DISEASE
PROTOCOL FOR CONTROLLED STUDY**

Secondary outcomes will be:

- Adverse events
- Patient laboratory parameters
- Patient Global Impression of change
- Work interference (Stanford Presenteeism Scale)

All other outcomes are exploratory.

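### Section 36 grades every adverse event by discomfort and disrupted activity alone, so a symptomless laboratory event has no grade or is logged as mild whatever its size

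*Combined protocol and SAP*

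**What the plan says.** Section 36 sits under the heading for non-serious events, but its wording reaches further: "Severity of all AEs will be graded on a three-point scale of intensity". The three levels are:

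- The lowest level reads "Mild: Discomfort is noticed, but there is no disruption of normal daily activities".
- The middle level asks for enough discomfort to interfere with ordinary life.
- The top level reads "Severe: Discomfort is incapacitating, with inability to work or to perform normal daily activities".

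Section 33 lists the known reactions to fresh frozen plasma. Among them: "Increase in serum creatinine level and/or acute renal failure have been observed". Lowered blood pressure appears there twice. The section calls the listed items adverse events and says that all instances, serious or not, will be reported.

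Section 8 names adverse events as a secondary outcome and, as a separate one, "Patient laboratory parameters". Section 17 schedules the blood tests at baseline and at weeks 4, 12 and 24, with extra tests only in response to adverse events. Section 34 ends the recording of non-serious events 14 days after study drug stops. Section 25 defers the full analysis plan, and Section 26 outlines the UPDRS analyses only.

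**The concern.** The scale measures how the patient feels and functions. That suits chills, headache or nausea. It does not suit an event whose importance lies in a measured value, and the protocol itself expects such events. Even the lowest level requires discomfort to be noticed, so a silent rise in creatinine falls under the rule without matching any level of it.

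This is more than missing detail, because the rule as written gives a wrong answer. A grader who must enter something will take the nearest level, and the phrase about undisturbed daily activities points to mild for a small change and a large one alike.

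Safety is a stated aim of the trial alongside efficacy (Section 7), though the primary outcome is UPDRS. With 10 patients per arm (Section 2), one patient is 1/10 = 10% of an arm, so one or two ungraded or misgraded events could alter any severity summary that is eventually produced. Nor do the documents say how the laboratory outcome will be turned into a statement about safety.

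**Working it through.** The plan gives no figure to reproduce. The check compares the definitions with the listed events, looks for another scale, and sets the recording window against the test dates.

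**1. Events against definitions**

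| Event (Section 33) | Mild: discomfort noticed | Moderate: activities affected | Severe: incapacitating | Definitions met |
|---|---|---|---|---|
| Creatinine rise, no symptoms | no | no | no | 0 of 3 |
| Blood-pressure fall, no symptoms | no | no | no | 0 of 3 |
| Either event with symptoms | can be graded | can be graded | can be graded | 1 of 3 |

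No level refers to a laboratory value, a vital sign or organ function.

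**2. Is there another scale?**

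- Section 37 assesses seriousness, causality and expectedness of serious events, not severity.
- Section 32 points to an outside circular but adopts no grading scale from it.
- Section 9, exclusion R, sets creatinine at 1.5 times the upper limit of normal. That is an eligibility limit at screening.
- Sections 8, 17 and 18 name the laboratory outcome, its schedule and the analytes. They give no threshold, reference range or shift rule.

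None of these grades a laboratory event.

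**3. How often can the rule meet a scheduled test?**

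Day 0 is allocation (Section 7). I assume that visit weeks and the infusion days in Section 11 are counted from day 0. Week 4 is then day 28, week 12 day 84 and week 24 day 168.

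- Section 7: first infusion at the latest on day 14, second on day 14 + 2 = 16, so the window closes by day 16 + 14 = 30.
- Section 11: first infusion at the latest on day 5, second on day 5 + 2 = 7, so the window closes by day 7 + 14 = 21.
- Day 28 lies inside the window only if the second infusion is on day 28 − 14 = 14 or later, so the first is on day 12 or later. Section 7 allows that on days 12 to 14 only; Section 11 never does.
- Days 84 and 168 lie outside under both.

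If visit weeks are counted from the first infusion instead, the window closes at 2 + 14 = 16 days, before the week-4 test at 28 days, and no scheduled test falls inside.

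Sections 7 and 11 disagree on the latest first infusion and must be reconciled; the result is given for both. Section 34 also speaks of recording throughout the trial before giving the 14-day limit, which leaves some ambiguity. I have taken the limit as binding. Blood tests prompted by an adverse event can fall inside the window on any reading.

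**The case against.** The strongest reply is that little is lost. A creatinine rise at week 4, 12 or 24 stays in the data as a number under the laboratory outcome, whatever grade it gets. Serious events are judged by other criteria. No severity table by arm is planned. The window keeps most or all scheduled tests out of non-serious event recording, and an extra test under Section 17 follows an event that has already been recorded. All of this stands, and it limits the point to severity grading and to the lack of an objective rule for summarising laboratory safety. It does not supply a grade for a symptomless event that is recorded.

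The blood-pressure part is weaker than the laboratory part. Section 33 lists low blood pressure among symptomatic reactions and does not call it silent, and the documents schedule no blood-pressure readings.

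A reader might infer two stronger things, and neither is supported:

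- *That the scale fails for every scheduled value.* Section 18 lists 25 analytes, and 25 × 20 patients × 3 post-baseline visits = 1,500 values. But Section 36 grades adverse events, not routine results, and two of the three visits lie outside the window. The product is not a count of ungraded events.
- *That the rule understates harm in the yFFP arm in particular.* The same scale applies to both blinded arms, and the documents give no reaction rates by arm. Such a bias would need silent laboratory reactions to be more frequent with plasma, which is not shown.

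**Conclusion.** The point holds in a limited form. Read literally, Section 36 leaves a symptomless laboratory adverse event without a grade. That such an event would be logged as mild regardless of size is an inference about how a grader would act, but the wording of the lowest level invites it.

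The size is modest: 20 patients, no planned analysis by grade, laboratory values kept as their own outcome, and a window that closes by day 21 or day 30. The number of events affected cannot be estimated from the documents. The conclusion assumes that no severity scale exists outside the text available here; the outside circular cited in Section 32 was not available. The change is worth making because it is cheap and also gives the laboratory outcome a summary that it now lacks.

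**What to change.** 1. In Section 36, limit the discomfort scale to symptomatic events.
2. Grade laboratory adverse events on the measured value, in bands relative to the patient's own baseline and the laboratory's upper or lower limit of normal. The lower limit is needed for analytes where a fall matters, such as hemoglobin or platelets. Fix the bands in the SAP before treatment codes are seen.
3. Apply the same bands to the scheduled week 4, 12 and 24 values, whether or not an adverse event was recorded, and tabulate the worst post-baseline grade by arm as the summary of the laboratory outcome in Section 8.
4. Grade blood-pressure events on the measured value only where a reading was recorded, since none is scheduled.

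Section 5 gives the trial as closed in January 2019, and the documents do not say whether treatment codes have been opened. If they have, the bands should be reported as set afterwards.

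The cost is one paragraph in Section 36, a short table of bands in the SAP, a small amount of extra analysis and a few more graded events. No new samples are required.
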